# 5.3.5.13 Adverse Events Associated with an Overdose or Error in Drug Administration

An overdose is the accidental or intentional use of a drug in an amount higher than the dose being studied. An overdose or incorrect administration of study treatment is not itself an adverse event, but it may result in an adverse event. All adverse events associated with an overdose or incorrect administration of study drug should be recorded on the Adverse Event eCRF. If the associated adverse event fulfills seriousness criteria or qualifies as an adverse event of special interest, the event should be reported to the Sponsor immediately (i.e., no more than 24 hours after learning of the event; see Section 5.4.1).

Any study drug overdose or incorrect administration of study drug should be noted on the Study Drug Administration eCRF.

The highest dose tested to date in patients with MS is 2000 mg, administered as two 1000-mg IV infusions separated by 2 weeks (Phase II dose finding study in RRMS). The adverse events were consistent with the safety profile for ocrelizumab in the pivotal clinical studies.

There is no specific antidote in the event of an overdose; interrupt the infusion immediately and observe the patient for IRRs.

## 5.4 IMMEDIATE REPORTING REQUIREMENTS FROM INVESTIGATOR TO SPONSOR

Certain events require immediate reporting to allow the Sponsor to take appropriate measures to address potential new risks in a clinical trial. The investigator must report such events to the Sponsor immediately; under no circumstances should reporting take place more than 24 hours after the investigator learns of the event. The following is a list of events that the investigator must report to the Sponsor within 24 hours after learning of the event, regardless of relationship to study drug:

- Serious adverse events, including serious IRR and serious MS relapse (see Section 5.4.1 for details on reporting requirements)
- Adverse events of special interest (see Section 5.4.1 for details on reporting requirements)
- Pregnancies (see Section 5.4.2 for details on reporting requirements)

The investigator must report new significant follow-up information for these events to the Sponsor immediately (i.e., no more than 24 hours after becoming aware of the information). New significant information includes the following:

- New signs or symptoms or a change in the diagnosis
- Significant new diagnostic test results
- Change in causality based on new information
- Change in the event's outcome, including recovery
- Additional narrative information on the clinical course of the event

Investigators must also comply with local requirements for reporting serious adverse events to the local health authority and IRB/EC.

# 5.4.1 Emergency Medical Contacts

Investigators will be provided with contact information for the Medical Monitor. An Emergency Medical Call Center Help Desk will be available 24 hours per day, 7 days per week. The Emergency Medical Call Center will connect the investigator with an Emergency Medical Contact, provide medical translation service if necessary, and track all calls. Contact information, including toll-free numbers for the Emergency Medical Call Center, will be distributed to investigators. Reporting Requirements for Serious Adverse Events and Adverse Events of Special Interest

# 5.4.1.1 Events That Occur prior to Study Drug Initiation

After informed consent has been obtained but prior to initiation of study drug, only serious adverse events caused by a protocol-mandated intervention should be reported. The paper Clinical Trial Adverse Event/Special Situations Form provided to investigators should be completed and submitted to the Sponsor or its designee immediately (i.e., no

more than 24 hours after learning of the event), either by faxing or by scanning and emailing the form using the fax number or email address provided to investigators.

# 5.4.1.2 Events That Occur after Study Drug Initiation

After initiation of study drug, serious adverse events and adverse events of special interest will be reported during the study through the end of the SFU period, which is at least 104 weeks after the last infusion but may be extended in patients whose B cells take longer to replete.

After this period, the investigator should notify the Sponsor of any serious adverse events, all deaths, and any serious adverse events that are believed to be related to prior study drug treatment (see Section 5.4.1.1). These events should be reported through use of the Adverse Event eCRF. A report will be generated and sent to Roche Safety Risk Management by the electronic data capture (EDC) system.

In the event that the EDC system is unavailable, the paper Clinical Trial Adverse Event/Special Situations Form provided to investigators should be completed and submitted to the Sponsor or its designee immediately (i.e., no more than 24 hours after learning of the event), either by faxing or by scanning and emailing the form using the fax number or email address provided to investigators. Once the EDC system is available, all information will need to be entered and submitted via the EDC system.

Instructions for reporting serious adverse events that occur after the last dose of study drug are provided in Section 5.6.

# 5.4.2 Reporting Requirements for Pregnancies

# 5.4.2.1 Pregnancies in Female Patients

Female patients of childbearing potential (and parent[s] or legal guardian, as applicable) will be instructed through the Informed Consent Form to immediately inform the investigator if they become pregnant during the treatment period or within 6 months after the last dose of study drug. The investigator should report the pregnancy on the Clinical Trial Pregnancy Reporting Form and submit the form to the Sponsor or its designee immediately (i.e., no more than 24 hours after learning of the pregnancy), either by faxing or by scanning and emailing the form using the fax number or email address provided to investigators. Pregnancy should not be recorded on the Adverse Event eCRF.

In the event of pregnancy, all infusions of ocrelizumab must be suspended until the completion of pregnancy and breastfeeding. The Investigator must counsel the patient as to the risks of continuing with the pregnancy and the possible effects on the fetus. Patients who are pregnant or breastfeeding should continue to follow the schedule of assessments for the study until conclusion of the pregnancy; however, no infusions will occur (see Section 4.3.6 and 5.1.5).
Any serious adverse events associated with the pregnancy (e.g., an event in the fetus, an event in the mother during or after the pregnancy, or a congenital anomaly/birth defect in the child) should be reported on the Adverse Event eCRF. In addition, the investigator will submit a Clinical Trial Pregnancy Reporting Form when updated information on the course and outcome of the pregnancy becomes available.

For pregnancies occurring in female patients during treatment with ocrelizumab or within 6 months after their last dose of ocrelizumab, the health status of the child will be followed until the child is 1 year of age (see Section 5.1.5).

#### 5.4.2.2 Abortions

A spontaneous abortion should be classified as a serious adverse event (as the Sponsor considers abortions to be medically significant), recorded on the Adverse Event eCRF, and reported to the Sponsor immediately (i.e., no more than 24 hours after learning of the event; see Section 5.4.1).

If a therapeutic or elective abortion was performed because of an underlying maternal or embryofetal toxicity, the toxicity should be classified as a serious adverse event, recorded on the Adverse Event eCRF, and reported to the Sponsor immediately (i.e., no more than 24 hours after learning of the event; see Section 5.4.1). A therapeutic or elective abortion performed for reasons other than an underlying maternal or embryofetal toxicity is not considered an adverse event.

All abortions should be reported as pregnancy outcomes on the paper Clinical Trial Pregnancy Reporting Form.

#### 5.4.2.3 Congenital Anomalies/Birth Defects

Any congenital anomaly/birth defect in a child born to a female patient exposed to study drug should be classified as a serious adverse event, recorded on the Adverse Event eCRF, and reported to the Sponsor immediately (i.e., no more than 24 hours after learning of the event; see Section 5.4.1).

#### 5.5 FOLLOW-UP OF PATIENTS AFTER ADVERSE EVENTS

#### 5.5.1 Investigator Follow-Up

The investigator should follow each adverse event until the event has resolved to baseline grade or better, the event is assessed as stable by the investigator, the patient is lost to follow-up, or the patient withdraws consent. Every effort should be made to follow all serious adverse events considered to be related to study drug or trial–related procedures until a final outcome can be reported.

During the study period, resolution of adverse events (with dates) should be documented on the Adverse Event eCRF and in the patient's medical record to facilitate source data verification. All pregnancies reported during the study should be followed until pregnancy outcome. In addition, the health status of the child will be followed until the child is 1 year of age. Data collection is voluntary only; it does not include any interventions or invasive procedures (see Section 5.1.5).

#### 5.5.2 Sponsor Follow-Up

For serious adverse events, adverse events of special interest, and pregnancies, the Sponsor or a designee may follow–up by telephone, fax, email, and/or a monitoring visit to obtain additional case details and outcome information (e.g., from hospital discharge summaries, consultant reports, autopsy reports) in order to perform an independent medical assessment of the reported case.

#### 5.6 ADVERSE EVENTS THAT OCCUR AFTER THE ADVERSE EVENT REPORTING PERIOD

After the end of the adverse event reporting period (defined as at least 104 weeks after the last infusion but may be extended in patients whose B cells take longer to replete), all deaths, regardless of cause, should be reported through use of the Long–Term Survival Follow–Up eCRF.

In addition, if the investigator becomes aware of a serious adverse event that is believed to be related to prior exposure to study drug, the event should be reported through use of the Adverse Event eCRF. However, if the EDC system is not available, the investigator should report these events directly to the Sponsor or its designee, either by faxing or by scanning and emailing the paper Clinical Trial Adverse Event/Special Situations Form using the fax number or email address provided to investigators.

#### 5.7 EXPEDITED REPORTING TO HEALTH AUTHORITIES, INVESTIGATORS, INSTITUTIONAL REVIEW BOARDS, AND ETHICS COMMITTEES

The Sponsor has a legal responsibility to notify regulatory authorities about the safety of a study treatment under clinical investigation. The Sponsor will comply with regulatory requirements for expedited safety reporting to regulatory authority (which includes the use of applicable systems, such as EudraVigilance), IRBs, ECs, and investigators.

The Sponsor will promptly evaluate all serious adverse events and adverse events of special interest against cumulative product experience to identify and expeditiously communicate possible new safety findings to investigators, IRBs, ECs, and applicable health authorities based on applicable legislation.

To determine reporting requirements for single adverse event cases, the Sponsor will assess the expectedness of these events using the Ocrelizumab Investigator's Brochure. The Sponsor will compare the severity of each event and the cumulative event frequency reported for the study with the severity and frequency reported in the applicable reference document.

Ocrelizumab—F. Hoffmann-La Roche Ltd 109/Protocol WA39085, Version 10 Reporting requirements will also be based on the investigator's assessment of causality and seriousness, with allowance for upgrading by the Sponsor as needed.

#### 6. STATISTICAL CONSIDERATIONS AND ANALYSIS PLAN

Because of the limited number of patients, all statistical analyses are purely descriptive and exploratory, and no formal hypothesis testing will be performed.

#### 6.1 DETERMINATION OF SAMPLE SIZE

The sample size of 6 patients per dose cohort was chosen on the basis of practical considerations and for feasibility.

#### 6.2 SUMMARIES OF DEMOGRAPHIC AND BASELINE CHARACTERISTICS

Demographic and baseline characteristics will be summarized using means, standard deviations, medians, and ranges for continuous variables and proportions for categorical variables, as appropriate. Summaries will be presented overall and by dose group and/or cohort.

Reasons for premature study withdrawal, enrollment, and major protocol deviations will be listed.

#### 6.3 ANALYSIS POPULATIONS

#### 6.3.1 Pharmacokinetic Analysis Population

Patients will only be excluded from the PK analysis population if they do not meet the inclusion or exclusion criteria, if they deviate significantly from the protocol, or if data are unavailable or incomplete, which may influence the PK analysis. Excluded cases will be documented together with the reason for exclusion.

#### 6.3.2 Safety Analysis Population

All patients who receive at least one dose of study medication will be included in the safety population. Patients will be grouped according to their dose group and/or cohort.

#### 6.4 REPLACEMENT FOR WITHDRAWALS

A minimum of 6 evaluable patients per dose level are required. Patients who are prematurely withdrawn before completion of the 24-week period for reasons other than safety may be replaced (i.e., added to the study and to the data set) in order to have sufficient data to inform the dose selection for the subsequent Phase III study in children and adolescents.

#### 6.5 PHARMACOKINETIC ANALYSES

Individual and mean serum–concentration–versus–time curves will be plotted. Individual PK parameters will be presented by listings and descriptive summary statistics for each dose. PK parameters will be estimated using non–compartmental methods (Cmax,

#### Ocrelizumab—F. Hoffmann-La Roche Ltd

110/Protocol WA39085, Version 10

minimum plasma concentration  $[C_{trough}]$ ), and a model–based approach (i.e., nonlinear mixed-effects modeling) will be used in addition (AUC). The relationship of selected PK parameters ( $C_{max}$  and AUC) with dose will be evaluated to investigate dose linearity, if different dose levels are assessed for the same body weight/age group. The relationship between individual exposure and age and body weight will be investigated. The relationship between individual ocrelizumab exposure and safety, PD (CD19 B–cell count), and exploratory parameters (e.g., ARR, IRRs, infections, adverse events) will be investigated.

#### 6.6 SAFETY ANALYSES

Safety data will be listed individually and summarized descriptively by cohort/dose level for the Dose Exploration period and the OOE. The exposure period (time at risk) for each safety endpoint is defined as time from the date of the first exposure to the study treatment to the date of study withdrawal or clinical cutoff date, whichever occurs earlier.

The safety endpoints include, but may not be limited to, the following:

- Incidence of adverse events (overall, by severity, and by relationship to study medication)
- Incidence of serious adverse events
- Incidence of treatment discontinuations due to adverse events
- Change from baseline by time in laboratory parameters and incidence of clinically significant laboratory abnormalities
- Change from baseline by time in vital signs (systolic blood pressure, diastolic blood pressure, pulse rate, respiratory rate, body temperature) and incidence of vital sign abnormalities

The incidence count for each adverse event will be defined as the number of patients reporting at least one treatment-emergent occurrence of the event. The incidence rate will be calculated as the incidence count divided by the total number of patients in each cohort as well as total. In addition, the rate per 100 patient-years (along with the 95% confidence interval using the exact method based on the Poisson distribution) will be calculated for all adverse events and serious adverse events.

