# 4.4 CONCOMITANT THERAPY

Concomitant therapy consists of any medication (e.g., prescription drugs, over-the-counter drugs, vaccines, herbal or homeopathic remedies, nutritional supplements) used by a patient in addition to protocol-mandated treatment from screening to the study completion/ discontinuation visit. All such medications should be reported to the investigator and recorded on the Concomitant Medications eCRF.

Concomitant medications will be reported at each visit in the relevant eCRFs starting from the baseline visit (including medication taken between screening and baseline). Any medications taken for the treatment of MS and any medications taken for the symptoms of MS prior to the baseline visit will be recorded at the baseline visit. Additionally, medications administered for any non–MS condition within 12 months prior to the baseline visit will also be recorded at the baseline visit.

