# 5.3.1 Adverse Event Reporting Period

Investigators will seek information on adverse events at each patient contact. All adverse events, whether reported by the patient or noted by study personnel or the MN staff, will be recorded in the patient's medical record and on the Adverse Event eCRF.

After informed consent and assent has been obtained but prior to initiation of study drug, only serious adverse events caused by a protocol-mandated intervention (e.g., invasive procedures such as biopsies, discontinuation of medications) should be reported (see Section 5.4.1 for instructions for reporting serious adverse events).

**After initiation of study drug**, all adverse events will be reported during the study through the end of the SFU period, which is at least *104* weeks after the last infusion but may be extended in patients whose B cells take longer to replete.

Instructions for reporting adverse events that occur after the adverse event reporting period are provided in Section 5.6.

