#### Appendix 1: Schedule of Activities

# Table 3 Safety Follow-Up (including Prolonged B-Cell Monitoring if Required)

	(at leas	Safety Follow-Up (at least $104$ weeks from the date of last infusion of ocrelizumab) a					Prolonged B–Cell Monitoring b	End of Observation or WD from SFU	Unscheduled Site or optional MN visit °			
Site Visits (weeks from the withdrawal from treatment visit) (± 7 days) a		24		48		72		96	104	Visits every 24 weeks (± 7 days)		
Site or opt mobile nursing visits (weeks from the withdrawal from treatment visit) (± 7 days) a	12		36		60		84					
Urine pregnancy test c	x	x										x
Routine safety laboratory d	x	х	х	х	x	x	x	x	x	x	x	x
Immunologic assessments e	х	х	х	х	x	x	x	x	x	x	x	(x)
Total Ig, IgA, IgG, IgM		х		х		x		x	x	x	x	(X)
ADA		x		х		x		x	x	x	x	
PK samples		х		х		x		x	x	x	x	
Plasma/Urine banking for JCV		x		x		x		x	x	x	x	(x)
Antibody titers		х		х		x		x	x	х	x	(x)
Hepatitis B Virus DNA f	(x)	(x)	(x)	(x)	(x)	(x)	(x)	(x)	(x)	(x)	(x)	
Vital signs	x	x	х	х	x	x	x	x	x	x	x	x
Neurological examination and EDSS		x		x		x		x	x	x	x	x
Physical examination g	x	х	х	х	x	x	x	x	x	x	x	x
SDMT		х		х		x		x	x	x	x	(X)
Visual testing (ETDRS and LCVA charts) h		x		x		x		x	x	x	x	(x)

**Ocrelizumab—F. Hoffmann-La Roche Ltd** 148/Protocol WA39085, Version 10

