### Table 3 Safety Follow-Up (including Prolonged B-Cell Monitoring if Required) (cont.)

Note: Marks in parentheses are optional and may be done as appropriate (e.g., if needs to be repeated).

a SFU will be carried out for at least 104 weeks starting from the date of last infusion of ocrelizumab.

Visits will be performed at 12-week intervals starting from the date of the patient's withdrawal from treatment visit or from the date of the Week 288 visit. At applicable sites, site visits will alternate with mobile nursing visits. SFU applies to study patients who have completed the treatment period (i.e., up to Week 288) and to patients who withdraw early from treatment. If B cells have returned to normal levels at the end of this SFU period, then the last scheduled SFU visit will become the end-of-observation visit, and the patient will have completed the study. Patients who receive alternative MS therapies that may change B-cell levels will only be followed up for a period of *104* weeks; they will not be entered into the prolonged B-cell monitoring period thereafter. A dedicated SFU visit directly prior to the start of an alternative MS treatment is required in order to assess patient's clinical status and safety.

- b Patients whose B cells have not returned to normal levels after *104* weeks of SFU will continue with site visits every 24 weeks (± 7 days) until B-cell repletion. Once B cells have returned to normal levels, patient will be scheduled for an end-of-observation visit, and the patient will have completed the study. Patients who begin during the prolonged B-cell monitoring period, alternative MS therapies that may change B-cell levels will only be followed up until the point they initiate this alternative MS therapy; an end-of-observation visit will be scheduled, and patients will have completed the study.
- c Urine β-hCG (sensitivity of at least 25 mlU/mL) test will be performed until 24 weeks after the last dose of ocrelizumab. Female patients of childbearing potential (e.g., in Tanner stages ≥ 2 or post-onset of menarche) must agree to remain completely abstinent or to use reliable means of contraception for 24 weeks after the last dose of ocrelizumab as described in Section 5.1.5). Confirmation by a serum pregnancy test will be performed for positive urine pregnancy test.

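### Section 6.6 does not end time at risk at study completion; read literally, the all-adverse-event rate per 100 patient-years is too low at any cutoff after some patients have completed

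*Combined protocol and SAP*

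**What the plan says.** Section 6.6 defines the exposure period for each safety endpoint as running from first exposure "to the date of study withdrawal or clinical cutoff date, whichever occurs earlier". The same section plans a rate per 100 patient-years, with an exact Poisson 95% confidence interval, for all adverse events and for serious adverse events. This definition therefore supplies the denominator. It was added in Version 10 at the FDA's request, according to the amendment rationale.

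Three places separate completion from withdrawal:

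- Appendix 1, Table 3, footnote a: if B cells have returned to normal by the end of follow-up, "then the last scheduled SFU visit will become the end-of-observation visit, and the patient will have completed the study".
- The same table heads a column "End of Observation or WD from SFU", naming the two exits as alternatives.
- Section 4.4 covers concomitant therapy "from screening to the study completion/ discontinuation visit".

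On collection of events, Section 5.3.1 says that once study drug has started, "all adverse events will be reported during the study through the end of the SFU period", which may be extended for slow B-cell repletion. After that, Section 5.4.1.2 reads "After this period, the investigator should notify the Sponsor of any serious adverse events, all deaths". Section 5.6 is narrower: it keeps all deaths and applies "if the investigator becomes aware of a serious adverse event that is believed to be related to prior exposure to study drug". Neither section asks for non-serious events.

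**The concern.** A patient who completes has no withdrawal date. Of the two end dates in Section 6.6, only the cutoff applies, so the clock runs on to the cutoff even though routine adverse event collection stopped at the end-of-observation visit. That time enters the denominator with no matching opportunity in the numerator for non-serious events. The error has one direction: the all-event rate and both confidence limits are too low, so the drug looks somewhat better tolerated than the data show.

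Two programmers could also derive different denominators from the same sentence, depending on whether they treat completion as a form of withdrawal.

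**Working it through.** **The plan's own duration.** Sections 3.1.1.1 and 3.1.1.4 give screening of at most 10 weeks, treatment of 288 weeks and follow-up of at least 104 weeks. 10 + 288 + 104 = 402 weeks, the participation stated in the Synopsis and Section 3.3. The figure is matched only if follow-up is counted from Week 288; from a last infusion at Week 264 the sum is 378. I therefore take T = 288 + 104 = 392 weeks from first dose to end of observation.

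**Room for staggered entry.** Section 3.2 gives about 11 years from first screening to last patient, last visit (LPLV), or about 574 weeks. 574 − 402 = 172 weeks, or 3.3 years. This is the longest accrual period that fits if every patient follows the 402-week course.

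**Formula.** Let x be the number of events and P the person-time. The rate is 100x/P, and the exact limits are chi-square quantiles depending only on x, divided by 2P. If a completer contributes L extra weeks after completion and no events, the rate and both limits are multiplied by T/(T + L). The factor does not depend on x. Pooled over patients, the understatement is 1 − (mean observed time)/(mean counted time).

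**Cutoff at LPLV, uniform entry.** The mean of L is half the accrual period.

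- 1 year: 1 − 392/418.1 = 6.2%
- 2 years: 1 − 392/444.2 = 11.7%
- 3.3 years: 1 − 392/478 = 18.0%

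**Earlier cutoffs.** Some patients are then still under observation, so mean observed time also falls. For 3.3 years of accrual and a cutoff 52 weeks before LPLV, mean counted time is 478 − 52 = 426 weeks. Mean observed time is 392 − 52²/(2 × 172) = 384.1 weeks, giving 1 − 384.1/426 = 9.8%. At 104 weeks before LPLV it is 1 − 360.6/374 = 3.6%.

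| Accrual | Cutoff at LPLV | 1 year earlier | 2 years earlier |
|---|---|---|---|
| 1 year | 6.2% | 0% | 0% |
| 2 years | 11.7% | 3.3% | 0% |
| 3.3 years | 18.0% | 9.8% | 3.6% |

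**Sensitivity to B-cell monitoring.** Events are still collected during prolonged monitoring, so that time is not excess. Section 1.2.4.2 gives an adult maximum of 175 weeks to repletion. If every patient is followed to Week 264 + 175 = 439, the room for staggered entry shrinks to 574 − 10 − 439 = 125 weeks. The LPLV figure becomes 1 − 439/501.5, about 12%. Extending the optional treatment period, which Section 3.1.1.3 allows, also lowers it.

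**Sensitivity to early stopping.** A patient who declines the extension at Week 24 and completes follow-up has T = 24 + 104 = 128 weeks and a longer unobserved tail. If 1 or 3 of 12 patients do so, with 172 weeks of accrual and a cutoff at LPLV, the pooled factor is 0.77 or 0.68 instead of 0.82. The 18% is therefore not a ceiling.

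**The case against.** The best defence is that study withdrawal here means any exit. Section 6.2, in the same statistical chapter, adds the word premature when it means early exit, so the unqualified term in Section 6.6 could be broader. Section 4.6.2 gives an open list of withdrawal reasons that includes study termination and site closure. Table 3 counts its visits from a withdrawal-from-treatment visit even for patients who finished Week 288. That reading may well be the intended one, but no passage states it, and footnote a to Table 3 points the other way. The defence leaves an ambiguity that the literal reading survives.

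It is also true that the documents give no cutoff date, entry pattern or number of completers for this study. Three of the nine cells above are zero. This limits any claim about the rate that will actually be reported, though not the point about the rule.

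A reader might infer three stronger things that the documents do not support:

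- That death is an equally clear omission. Death is not named in Section 6.6, but the list in Section 4.6.2 is open, so it could be coded as withdrawal.
- That Section 6.6 contradicts itself because safety data are "summarized descriptively by cohort/dose level for the Dose Exploration period and the OOE" while time at risk runs into follow-up. That sentence governs the period summaries; the event window for the rate is simply not spelled out. Restricting the rate to those two periods would discard the follow-up that Version 10 lengthened in the same amendment.
- That the safety conclusions or the dose choice are compromised. Patient-based proportions (which Section 6.6 calls incidence rates) do not use person-time. Dose selection rests on the monitoring committee's review of pharmacokinetic, pharmacodynamic, safety and tolerability data, not on this rate. There is no comparator, and Section 6 makes all analyses descriptive.

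**Conclusion.** The point holds in a conditional form. If Section 6.6 is programmed as written and the cutoff falls after some patients have completed, the all-event rate per 100 patient-years and both Poisson limits are too low. The documents do not determine by how much. It is 0% if the cutoff precedes the first completion. It is about 6% to 18% at LPLV under uniform entry over 1 to 3.3 years with everyone observed to Week 392, and about 12% at the longest accrual that fits if all are monitored to Week 439. The serious-event rate is less affected, because some serious events are still reported after completion.

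Severity is minor. Confidence is high on the wording and moderate on whether the reported rate will be affected.

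**What to change.** In Section 6.6, end time at risk at the earliest of study completion (the end-of-observation visit), study withdrawal (last contact if lost to follow-up, with death named for clarity) or the clinical cutoff date. Count in the rate only events with onset inside that window, so that numerator and denominator match. Serious events reported later under Sections 5.4.1.2 and 5.6 can be listed separately.

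The cost is a sentence or so, using dates already collected. Where the cutoff follows some completions, the reported all-event rate will be slightly less favourable than under the literal rule. Because the definition was added at the FDA's request, and the text of that request is not in the documents, the change of wording should be notified.
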